4.3.5.2 Rescue therapy related exploratory endpoint analysis

- Time-to-first instance rescue therapy (composite) of receiving RBC transfusions, or erythropoietin analogue as rescue therapy will be analysed analogously as Time to first RBC transfusion in Section 4.3.4. The OT+3 will be used.
- Number of rescue therapy treatments given; RBC transfusion or erythropoietin analogue per PEY will be reported descriptively, together and separately. The OT+3 will be used.
- Proportion of subjects receiving RBC transfusion during week 28 to week 52 will be analysed using Miettinen & Nurminen model adjusting for the region, history of CV and baseline Hb (≤ 8 , > 8 g/dL) and dialysis duration, comparing roxadustat to epoetin alfa. The OT+3 will be used.

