The need for RBC transfusion as rescue therapy in subjects treated with roxadustat as compared to epoetin alfa	Time-to-first (and proportion of subjects receiving) administration of red blood cell (RBC) transfusion as rescue therapy

Secondary Safety Objectives:	Outcome Measure:
To evaluate the safety and tolerability of roxadustat.	Adverse events (AEs), serious adverse events (SAEs). Changes in vital signs, electrocardiogram (ECG) and laboratory values.

Target subject population

Approximately 2000 anemic patients with chronic kidney disease (CKD) receiving hemodialysis or peritoneal dialysis with an indication for treatment with an erythropoietin analogue.

Duration of treatment

The study will consist of three study periods as follows:

- **Screening Period:** Up to 6 weeks
- **Treatment Period:** Patients will be randomized (1:1) to open-label treatment with either roxadustat or epoetin alfa. A study end date will be declared and common close-out will occur when the target number of CV events has been accrued. The expected duration of treatment is estimated to be up to 4 years
- **Post-Treatment Follow-Up Period:** 4 weeks

Investigational product, dosage and mode of administration

Roxadustat

Roxadustat will be administered orally three times a week (TIW). Study drug doses must be administered at least 2 days apart but no more than 4 days apart (e.g., Monday, Wednesday, Friday). Selection of roxadustat starting dose will utilize a conversion table (Section 7) for patients currently treated with an erythropoietin analogue. Patients not currently treated with an erythropoietin analogue will initiate roxadustat using a tiered weight-based dosing scheme. Patients with dry weights between 45 and 70 kg will receive 70 mg of roxadustat as starting dose. Patients with dry weights between 71 and 160 kg will receive 100 mg of roxadustat for initial dosing. Dose adjustments are permitted starting at week 4 and at intervals of every 4 weeks thereafter in order to achieve an Hb level of 11 g/dL and maintain an Hb of 11±1 g/ dL . However, dose adjustments can be done at any time if dose reduction is required for excessive erythropoiesis. Study drug will be dosed TIW throughout the study treatment period unless downward dose adjustment requires a change to twice or once weekly.

Epoetin alfa

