7.7.4.2 Erythropoietin analogue administration in patients randomized to roxadustat

For patients randomized to roxadustat, the investigator may initiate use of an approved erythropoietin analogue if all of the following criteria are met:

- A patient's Hb level has not sufficiently responded to two or more dose increases or the maximum dose limit of the study drug has been reached, and
- The patient's Hb is <8.5 g/dL on two consecutive measurements drawn at least five days apart; and
- Clinical judgment does not suggest iron deficiency or bleeding as a cause of lack of response or rapid decline in Hb (see 7.7.4.1 and 7.7.4.2 above for addressing these conditions), and
- Reducing the risk of all immunization in transplant eligible patients and/or reduction of other RBC transfusion-related risks is a goal

The patient is not allowed to be administered both an erythropoietin analogue and study drug at the same time. Treatment with an erythropoietin analogue should be stopped when Hb >9 g/dL or after a 4-week cycle has been completed, whichever comes first. Study treatment should be resumed after the following intervals:

- Two days after stopping epoetin
- One week after stopping darbepoetin alfa
- Two weeks after stopping methoxy polyethylene glycol-epoetin beta (Mircera)

If more than one cycle of erythropoietin analogue rescue is required, the investigator should permanently discontinue study drug. Use of erythropoietin analogues will be recorded in the eCRF.

Note: For patients randomized to epoetin alfa, the investigator may initiate use of a different erythropoietin analogue if clinically indicated. Use of the different erythropoietin analogue will be recorded in the eCRF and will be considered rescue therapy.

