4.1.1 Censoring

For analyses based on OT+7, subjects will be censored at 7 days after last intake of study drug, or the EOS visit, whichever is earliest.

For analyses based on OT+3, subjects will be censored at 3 days after last intake of study drug, or the EOS visit, whichever is earliest.

For analyses based on OT+0, subjects will be censored at last intake of study drug, or the EOS visit, whichever is earliest.

For analyses based on the ITT analysis set and FAS, subjects will be censored at their individual EOS visit, regardless of if they have discontinued study drug or not. Complete endpoint information will be pursued with every effort for all subjects, unless they exercise their right to withdraw consent. Subjects who withdraw consent will be censored at date of withdrawal of consent, and subjects who are lost to follow up (LTFU) will be censored at last available contact.

Subjects who withdraw consent and for whom only vital status (known to be alive at study closure, or date of death) may be obtained from public records, the occurrence of all components of the primary endpoint cannot be assessed, and will thus be censored at date of consent withdrawn for all analyses. However, the determination of all-cause death will utilize all publicly known mortality data, even that extending beyond date of consent withdrawal. The vital status information will be included in the analysis of all-cause death as a single endpoint, and in sensitivity analysis and tabulations. Similarly, complete information on the endpoint may not be obtained for subjects who are LTFU. Any such subject will be censored in the analysis at the last contact where all elements of the endpoint were assessed. A subject

will not be recorded as LTFU until the end of the study, after every allowable effort to get in contact has been made. Hence, it is anticipated that the number of subjects LTFU will be limited.

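### Under OT+3, an ESA rescue starting more than 3 days after the last roxadustat dose counts only if roxadustat is later resumed, so the exploratory rescue analyses can understate the roxadustat rate

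*SAP*

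**What the plan says.** SAP 4.3.5.2 defines two exploratory analyses that include ESA as rescue. One is the time to the first transfusion or ESA, handled like the time to first transfusion in SAP 4.3.4. The other is the count: "Number of rescue therapy treatments given; RBC transfusion or erythropoietin analogue per PEY will be reported descriptively, together and separately. The OT+3 will be used". Both use OT+3, for which SAP 4.1.1 sets the limit: "subjects will be censored at 3 days after last intake of study drug, or the EOS visit, whichever is earliest".

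Protocol 7.7.4.2 governs ESA rescue in the roxadustat arm:

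- Overlap is barred: "The patient is not allowed to be administered both an erythropoietin analogue and study drug at the same time".
- A cycle is bounded: "Treatment with an erythropoietin analogue should be stopped when Hb >9 g/dL or after a 4-week cycle has been completed, whichever comes first".
- Roxadustat is then expected to restart: "Study treatment should be resumed after the following intervals", ranging from two days to two weeks by agent.
- A further cycle ends treatment: "If more than one cycle of erythropoietin analogue rescue is required, the investigator should permanently discontinue study drug".

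Protocol 5.1.1.2 and SAP 4.1.3 count ESA as rescue in the roxadustat group only. A note at the end of Protocol 7.7.4.2 also treats a switch to a different ESA in the epoetin alfa arm as rescue.

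**The concern.** ESA rescue and roxadustat cannot run together, so each ESA cycle starts after some roxadustat dose. Whether the cycle falls inside OT+3 then depends on whether that dose was the subject's last. If roxadustat is resumed, the last intake moves past the cycle and the rescue counts. If it is not resumed, the window shuts 3 days after the dose that preceded the rescue. Inclusion of an event thus depends on what happens after it, and the rescues at risk of being dropped are among those that end treatment.

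In the composite, a missed first rescue becomes a censored observation in a subject who was about to have the event, which is informative censoring. In the per-PEY count it is a lost event. Where ESA counts as rescue for roxadustat only, the loss falls on that arm and lowers the hazard ratio. SAP 4.1.3 still attaches a non-inferiority margin of 1.8 to this composite, so the error would run towards the favourable conclusion.

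**Working it through.** The plan states no rate, event count or power for ESA rescue, so there is no figure of its own to reproduce. The check traces the counting rule and then shows how any loss would act.

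**1. Rule.** Let L be the last study drug intake overall. Under OT+3 an ESA rescue counts if its start day is at most L + 3 (and not after EOS).

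**2. Records (illustrative days).**

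| Record | L | Limit L + 3 | ESA start | Counted? |
|---|---|---|---|---|
| A. Roxadustat to day 200, resumed day 232 | 232 or later | 235 or later | 204 | Yes |
| B. Roxadustat to day 200, never resumed | 200 | 203 | 204 | No |
| C. Roxadustat to day 200, never resumed | 200 | 203 | 202 | Yes |
| D. Second cycle after resumption, last dose on day D | D | D + 3 | D + 4 | No |

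A and B are the same rescue and differ only in later resumption. C shows that a treatment-ending rescue starting on days 1 to 3 is counted. In D the first cycle has already supplied the composite event, so only the per-PEY count loses anything.

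**3. Cycle or administration.** SAP 4.3.5.2 does not say which one a treatment is. Assume epoetin three times a week for 28 days (12 doses, spaced 2, 2 and 3 days) in a cycle not followed by resumption. A start on day 1 puts 2 of 12 doses inside the window, a start on day 2 or 3 puts 1 of 12, and a start on day 4 or later puts none. With resumption, all 12 count.

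**4. Can the gap exceed 3 days?** The Protocol synopsis says: "Study drug doses must be administered at least 2 days apart but no more than 4 days apart". Three doses a week with gaps of at least 2 days use 6 of 7 days, so a fixed weekly schedule is 2, 2 and 3 days. ESA given in place of the next dose would then usually start on day 2 or 3, inside the window. A 4-day gap is permitted but needs a shifted schedule. On the other side, Protocol 7.7.4.2 asks for two low Hb readings at least five days apart and sets no interval between the last roxadustat dose and the first ESA dose. If roxadustat were stopped at the first low reading, ESA would start on day 5 or later. The documents do not say which pattern is typical.

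**5. How a loss would act (all inputs assumed).** Let q be the share of ESA rescues never followed by resumption, and u the share of those starting after day 3. Share captured = 1 − q × u:

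- q = 0.10, u = 0.25: 1 − 0.025 = 97.5%
- q = 0.50, u = 0.50: 1 − 0.25 = 75%
- q = 0.50, u = 1: 1 − 0.50 = 50%

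For the composite, let s be the ESA share of first rescues on roxadustat and m = q × u the share of those missed. With rare events and losses on roxadustat only, observed HR ≈ true HR × (1 − s × m). Taking a true HR of 1.8:

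- s = 0.10, m = 0.10: 1.8 × 0.99 = 1.78
- s = 0.25, m = 0.25: 1.8 × 0.9375 = 1.69
- s = 0.50, m = 0.50: 1.8 × 0.75 = 1.35

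These show direction and sensitivity. They are not estimates for this trial.

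**6. Is the loss recovered elsewhere?** SAP 4.3.6 repeats the transfusion endpoint on ITT, and the primary and secondary endpoints on OT+7. Neither repeat reaches the exploratory composite or the ESA count. SAP 4.3.5.5 describes ESA started after discontinuation, but does not add it to the rescue rate.

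**The case against.** The case for leaving the plan alone has weight. An on-treatment focus is a deliberate choice. The protocol directs resumption after a first cycle, and every resumed cycle is counted. Ordinary dose spacing puts a substituted ESA dose inside the window. The count is descriptive, the composite is exploratory, and SAP 4.2.2 says everything outside the confirmatory sequence is read descriptively; the rescue endpoint in that sequence is transfusion alone. ESA begun after discontinuation stays visible in SAP 4.3.5.5. Protocol 3.9.3 provides for conventional therapy after permanent discontinuation, so some of that ESA may not be rescue at all.

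This limits the scale and the stakes. It does not remove the dependence on later resumption or the informative censoring, and no planned repeat addresses either.

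Three stronger readings are tempting and unsupported. A reader might infer that every treatment-ending rescue is lost, but starts on days 1 to 3 are counted. A reader might infer that ESA rescue enters the analysis nowhere else, but it also enters the EU primary endpoint, the sensitivity analysis of the US primary that drops Hb after rescue, and the exploratory Hb response. And a reader might put a percentage on the loss, but the documents give neither the resumption rate nor the timing of ESA.

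**Conclusion.** The point stands in a limited form. ESA rescues that start more than 3 days after the last roxadustat dose and are not followed by resumption drop out of the composite and the per-PEY count; identical rescues followed by resumption do not. A second cycle can be missed in the per-PEY count only. The likely effect is a roxadustat rescue rate and a composite hazard ratio that are too low, by an amount that cannot be estimated from the documents.

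The direction rests on ESA rescue being counted for roxadustat only. If the note in Protocol 7.7.4.2 governs instead, an epoetin alfa subject who switches and does not return can be lost in the same way, and the direction is less certain. No confirmatory conclusion depends on either analysis, but the correction is cheap enough to be worth making.

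**What to change.** In SAP 4.3.5.2 and 4.3.6, add a repeat of the composite and the per-PEY count without the 3-day cut-off, shown beside OT+3. Two versions would serve:

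- ITT, as already planned for transfusion.
- One extended window, such as last intake plus 28 days. Protocol 3.9.3.2 uses 28 days to capture adverse events and potential endpoints after discontinuation; it is a convenient anchor, not a defined rescue window.

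Whichever is chosen must apply identically to both arms, to transfusion and ESA, to the censoring of event-free subjects and to the PEY denominator. Lengthening the window for roxadustat ESA alone would create a new asymmetry. Count only ESA recorded in the eCRF as rescue.

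The SAP should also:

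- reconcile whether a different ESA in the epoetin alfa arm counts as rescue (Protocol 7.7.4.2 against Protocol 5.1.1.2 and SAP 4.1.3);
- say whether a treatment is a cycle or an administration;
- align SAP 3.1.6.2, which lists transfusion only, with SAP 4.3.5.2.

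The cost is SAP wording and modest programming. Rescue use is already recorded, and Protocol 3.9.3.2 asks for anemia treatment after discontinuation to be documented. The downside is that some ESA courses must be classified as rescue or as ordinary care after discontinuation, which in an open-label trial relies on investigator labelling.

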2.1.3 Safety Analysis Set

All subjects who received at least one dose of randomized study drug will be included in the Safety Analysis Set. Throughout the safety results sections, erroneously treated subjects will be accounted for in the actual treatment group. If a subject has received both treatments, only the initial period will be utilized. Subjects will be censored at either, 7, 3 or 0 days after last intake of study drug. Consequently, there will be three versions of the Safety Analysis Set, and they will be referred to as On-treatment+7 (OT+7), OT+3 and OT+0 respectively.

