3.1.6.2 RBC transfusion related exploratory variables

- Number of rescue therapy treatments given, RBC transfusion per patient exposure year (PEY).
- Proportion of subjects with RBC transfusions during week 28 to week 52.

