4.2.4 Difference in proportions analysis

For analysis of difference in proportions the approach by [Miettinen & Nurminen 1985](#) will be used and a 2-sided 95% confidence interval for the difference of two proportions (roxadustat vs epoetin alfa) will be computed, adjusting for stratification factors. The model will include the terms of baseline Hb, treatment group, cardiovascular history, geographic region and dialysis duration. The stratified statistics will be based on the standard normal statistic proposed by Gart and Nam 1990.

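### As written, the week 28-52 transfusion proportion on OT+3 scores subjects who stopped drug before week 28 as transfusion-free, so it is understated and, if early stopping differs by arm, biased between arms

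*SAP*

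**What the plan says.** SAP 3.1.6.2 defines the variable only as "Proportion of subjects with RBC transfusions during week 28 to week 52". SAP 4.3.5.2 gives the analysis: "Proportion of subjects receiving RBC transfusion during week 28 to week 52" is to be compared by the Miettinen & Nurminen method, adjusted for region, CV history, baseline Hb and dialysis duration. On the analysis set it says "The OT+3 will be used".

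OT+3 is defined in two places. SAP 2.1.3 says "All subjects who received at least one dose of randomized study drug will be included in the Safety Analysis Set" and that "there will be three versions of the Safety Analysis Set, and they will be referred to as On-treatment+7 (OT+7), OT+3 and OT+0". SAP 4.1.1 adds the cut-off: "For analyses based on OT+3, subjects will be censored at 3 days after last intake of study drug", or at the EOS visit if that comes first.

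The method is in SAP 4.2.4: "a 2-sided 95% confidence interval for the difference of two proportions (roxadustat vs epoetin alfa) will be computed", with stratification. It contains no censoring or exposure term.

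Neither 3.1.6.2 nor 4.3.5.2 requires a subject to be on drug, or under observation, at week 28. By contrast, SAP 3.1.2 does exclude subjects with no Hb measurement from week 28 for the two week 28-52 variables on time in an Hb range.

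**The concern.** A difference in proportions needs each subject classed as event or no event over the same window. OT+3 cannot supply that for a window opening at week 28. A subject whose last dose was more than 3 days before week 28 has no OT+3 time in the window, yet belongs to the set. Under the written definitions that subject can only be a non-event. A subject who stops inside the window without an earlier in-window transfusion is also a non-event, on partial observation.

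The reported figure then mixes transfusion risk with the rate of stopping drug. The trial is open-label, and Protocol 3.9.2 lists one reason for permanent discontinuation that applies to roxadustat only (need for a second cycle of erythropoietin analogue rescue), so unequal stopping is possible. Subjects who stop for that reason are poor Hb responders and may be more likely to need transfusion. At stake is the reading of one descriptive comparison: a lower proportion could reflect more discontinuation rather than less transfusion need.

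**Working it through.** **The plan's own figure.** The documents state no power, precision or expected rate for this endpoint. Their only power statement is for the primary Hb endpoint (SAP 1.3): 600 subjects, assumed difference -0.30, margin -0.75, SD 1.25 g/dL, at least 99% power. With 300 per arm, (0.75 - 0.30) / (1.25 × √(2/300)) = 0.45 / 0.102 = 4.41, and 4.41 - 1.96 = 2.45, giving 99.3%. It reproduces, but has no bearing on this point.

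**Inputs.** From the documents: about 2000 subjects randomised 1:1, so about 1000 per arm; OT+3 membership and cut-off; the method. Assumed, because the documents give nothing: q, the week 28-52 transfusion risk among subjects on drug at week 28, taken equal in both arms at 3%, 6% or 10%; and d, the share of dosed subjects who stop before week 28, between 10% and 30%.

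**Formula.** Counting every dosed subject, the reported proportion is q(1 - d). With equal q, the ratio between arms is (1 - d₁)/(1 - d₂), whatever q is. Arm 1 is the arm that stops more.

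| Stopped before week 28, arm 1 / arm 2 | Ratio | q = 3% | q = 6% | q = 10% |
|---|---|---|---|---|
| 10% / 10% | 1.000 | 2.70 v 2.70 | 5.40 v 5.40 | 9.00 v 9.00 |
| 15% / 10% | 0.944 | 2.55 v 2.70 | 5.10 v 5.40 | 8.50 v 9.00 |
| 20% / 10% | 0.889 | 2.40 v 2.70 | 4.80 v 5.40 | 8.00 v 9.00 |
| 25% / 15% | 0.882 | 2.25 v 2.55 | 4.50 v 5.10 | 7.50 v 8.50 |
| 30% / 15% | 0.824 | 2.10 v 2.55 | 4.20 v 5.10 | 7.00 v 8.50 |

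Where stopping is unequal, the spurious difference runs from -0.15 to -1.50 percentage points. With equal stopping it is zero, but both arms are too low.

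**Against sampling error.** For 25% / 15% and q = 6%, the standard error is √(0.045 × 0.955/1000 + 0.051 × 0.949/1000) = 0.96 points, against a gap of 0.60. For q = 10% it is 1.21 points against 1.00. By normal approximation, the chance of a nominal two-sided p < 0.05 with no true difference is 9.6% and 13.1% in these two cases. Over all the unequal cases in the table it runs from 5.5% to 24%, instead of 5%.

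**Masking.** The same effect can hide a real excess. With 25% / 15% stopping, an on-drug risk ratio of 0.85/0.75 = 1.13 against arm 1 would appear as no difference.

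**What follow-up after stopping would show.** Suppose stoppers are transfused at 1.5 times q, with q = 6%, so 9%. For 25% / 15%: 0.75 × 6% + 0.25 × 9% = 6.75%, against 0.85 × 6% + 0.15 × 9% = 6.45%. The sign reverses from the 4.5% versus 5.1% reported on OT+3. If stoppers have the same risk as the rest, both arms show 6.0%.

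Stopping inside the window is not in these figures; it would lower the proportions further.

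**The case against.** **The denominator is inferred.** The endpoint bullet does not state one, and a programmer might drop subjects with no in-window OT+3 time. That stands as a caution: the SAP does not say outright that early stoppers are scored as transfusion-free. But the set definition puts them in, the method has no way to censor them, and the SAP writes an exclusion for the Hb time variables while writing none here. Following the text leaves them in the denominator.

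**Nothing confirmatory depends on it.** This is correct. SAP 4.2.2 treats everything outside the testing sequence as descriptive, and this endpoint carries no margin.

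**The question is covered elsewhere.** It is in part. The preceding bullet of SAP 4.3.5.2 gives rescue treatments per patient-exposure-year. The secondary time-to-first analysis uses a Cox model, with Kaplan-Meier estimates under SAP 4.2.3 and an ITT repeat under SAP 4.3.6. None of these is specific to weeks 28-52, and the ITT repeat names only the secondary endpoint.

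**The bias may be small or absent.** This is also fair. It needs unequal stopping, every rate above is assumed, and in the 25% / 15% cases the gap is below one standard error.

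**Restricting to subjects on drug at week 28 has its own problem.** It conditions on something that happens after randomisation and can introduce selection between arms. That stands, and is why it should not be the main analysis.

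**Conclusion.** The point holds as a minor flaw of analysis choice. Applied as written, the OT+3 proportion is q(1 - d) in each arm: too low in both, and tilted toward the arm with more early stopping when stopping differs and other things are equal. For 25% versus 15% stopping the ratio is 0.88, or 0.6 to 1.0 points at on-drug risks of 6% to 10%. All stopping and transfusion rates are assumptions.

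Three stronger readings are not supported:

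- A reader might infer that roxadustat will look better. The documents give no stopping rates; the roxadustat-only discontinuation rule shows a route to imbalance, not its size or net direction.
- A reader might infer that the secondary non-inferiority test on transfusion is affected in the same way. That test is on the Cox hazard ratio (SAP 4.3.4, item 7), which censors early stoppers instead of counting them as event-free.
- A reader might infer that the flaw is confined to the windowed endpoint. It is not: the proportion of subjects transfused that accompanies the secondary time-to-first endpoint is also on OT+3 and, if reported as a crude proportion, has the same limitation.

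**What to change.** In SAP 4.3.5.2:

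1. Analyse the week 28-52 transfusion proportion on the ITT set, with follow-up regardless of drug stopping, and state how deaths and withdrawals before or during the window are counted.
2. Present the OT+3 version as a Kaplan-Meier estimate for the window among subjects whose OT+3 period reaches week 28. Show the numbers at risk at week 28 by arm, and label it as conditional on a post-randomisation event.
3. Note beside the crude proportion in SAP 4.3.4, item 7, that it takes no account of differing on-drug observation time.

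The cost is a few sentences and a little extra programming. The ITT version depends on transfusions being recorded after drug is stopped. Protocol 3.9.3.2 asks for anemia treatment after discontinuation to be documented, and SAP 4.3.6 already plans an ITT transfusion analysis, so the data should largely exist, but some may be incomplete. The number of subjects with incomplete follow-up in the window should be reported by arm.
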